6.0 SUMMARY OF GENERAL STUDY DATA

6.1 Subject Disposition

Subject disposition data is collected on the 'Disposition - Phase 1 Completion Status', 'Disposition - Phase 2 Completion Status', and 'Disposition – End of Study' CRF pages. The summary of the number of subjects enrolled, screen failure, randomized and not treated, randomized and treated, ITT subjects, completed the study, and discontinued from the study by reason of discontinuation will be provided. Screen failures will be summarized for each inclusion/exclusion criteria that were not met.

6.2 Protocol Deviations

The number of subjects with protocol deviations for the ITT subjects will be summarized with descriptive statistics by the nature of the deviation. The major or minor deviations will be identified and classified as in Appendix 3 prior to data analyses of major reporting.

6.3 Demographics and Baseline Variables

Demographics and baseline characteristics will be summarized with descriptive statistics for the ITT population. Summary statistics for categorical variables will include frequency counts and percentages and for continuous variables will include mean, standard deviation, minimum, median, and maximum.

Demographics and baseline characteristics variables include:

- Age at time of Informed Consent (years)
- Sex (Female)
- Ethnicity (Hispanic or Latino, Not Hispanic or Latino, Not Reported, and Unknown)
- Race (American Indian or Alaskan Native, Asian, Black or African American, Native Hawaiian or Other Pacific Islander, White, Not Reported, and Unknown)
- Medical history
- 6.4 Device Failure, Malfunctions and Defects

All device deficiencies will be summarized by the failure code for the ITT population.

7.0 SAFETY ANALYSIS

Adverse Events (AEs) and Serious Adverse Events (SAEs) data will be presented based on treatment phases: the PureWick Phase includes all AEs/SAEs that occurred during the PureWick treatment phase, and the Hollister Phase includes all AEs/SAEs that occurred during the Hollister treatment phase. AEs/SAEs that occurred during the washout period will

RD	Statistical Analysis Plan	Page No. 18 of 20
	Study ID: UCC-8007	Version No: 01

be included in the analysis for the device used in Phase 1 treatment if treatment was performed for phase 1. If treatment was not performed in one of the phases, the AEs will be included in the other phase where treatment was performed for the subject.

Statistical Analysis Plan	Page No. 19 of 20
Study ID: UCC-8007	Version No: 01

INTERIM ANALYSIS PLAN 8.0

Not applicable.

REFERENCES 9.0

None.

10.0 **APPENDIX**

- Appendix 1 Appendix 2 Appendix 3
- Tables, Figures and Listing Shells Derived Data Specification Protocol Deviations: Major/Minor Classification

R D	Statistical Analysis Plan	Page No. 20 of 20
	Study ID: UCC-8007	Version No:
		01

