4.0 STUDY DESIGN

4.1 Overall Design

In this prospective, post-market, multi-site, open-label, crossover trial, women with urinary incontinence requiring the use of diapers (changes complets (Fr)) at night will be 1:1 randomized to a treatment sequence using two devices (PureWick[™] System and Hollister® Female Urinary Pouch External Collection Device) and followed for approximately 10 weeks through 2 treatment phases.

Approximately 30 female participants from 2 sites will be enrolled into the study. Those meeting eligibility criteria will be treated according to the treatment sequence assigned during randomization. Participants will be trained by the nurses for the applicable product at the beginning of each treatment phase and have access to the IFU to review during each treatment phase. The total expected duration of subject participation is approximately 10 weeks. Participants will use the device assigned in treatment phase 1 overnight while sleeping for 4 weeks (28 days) before transitioning to the second assigned device in treatment phase 2. There will be a minimum washout period of 2 weeks (not to exceed 4 weeks) between treatment phases and a re-screening of eligibility criteria before the second phase. Participants assigned to both treatment arms will place and remove the FEC (female external catheter) or FUP (Female Urinary Pouch) after standardized teaching is completed on the first day of the treatment phase.

The primary objectives are to evaluate safety (skin injury) and efficacy (capture rate). Safety will be assessed using the Draize Scale and efficacy will be measured based on daily urine capture rate. Nurses will visit participants' homes daily to perform a skin assessment and collect urine measurements during the treatment phases. Participants will be withdrawn from the treatment phase if grade 4 is achieved in any category on the Draize skin irritation scale.

The secondary objectives are to assess quality of life, tolerability, preference, comfort and ease of use. Quality of life will be measured using self-reported changes in quality of life via the validated Nocturia Quality of Life (N-QOL) and PROMIS Sleep Disturbance assessments. Preference, comfort and ease of use will be measured using subjective evaluations of the therapy via participant surveys. Tolerability will be measured by number of days of actual use of both devices, and discontinuation rate attributed to the device's discomfort or inconvenience.

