7.2.7 Days 2-7

- 1. Prior to nurse visit, participants are expected to have placed the used night pads and mesh underwear (if applicable) in their respective labeled, pre-weighed sealed bag upon completion of sleep.
- 2. Nurse will weigh and document weight of night pads and mesh underwear (if applicable).
- 3. The nurse will weigh and document the captured urine.
 - For PureWickTM Treatment Phase the captured urine volume in the PW urine collection canister will be weighed and documented.
 - For Hollister_® FUP Treatment Phase the captured urine volume in the bedside urine bag will be emptied into a graduated cylinder, then weighed and documented.
- 4. The nurse will note any signs of skin irritation or injury and document the Draize Scale score*
- 5. If during the skin assessment a Draize score of 4 is documented on the skin irritation scale in any category, this must be recorded as an AE and will require participants to discontinue from the treatment phase; participant will immediately begin wash out period and complete N-QoL.
- 6. Nurse will pre-weigh and document weight of study supplies for next night use.
- 7. The nurse will confirm the next day visit.

* For safety assessment, see section 7.3

7.2.8 Day 8

- 1. Same procedures as days 2-7.
- 2. Participant to complete Day 8 PROMIS Sleep Disturbance assessment.

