8.0 PARTICIPANT DISCONTINUATION/WITHDRAWAL

8.1 Discontinuation/Withdrawal

- A participant may withdraw from the study at any time at his/her own request or may be withdrawn at any time at the discretion of the investigator or sponsor for safety, behavioral, compliance, or administrative reasons. This is expected to be uncommon.
- At the time of discontinuing from the study, no further assessments will be performed.
- If the participant withdraws consent for disclosure of future information, the sponsor may retain and continue to use any data collected before such a withdrawal of consent.
- Participants who withdraw or discontinue the study early may be replaced.

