2.0 STUDY DESIGN

2.1 Study Design

This is a prospective, open-label, 2 by 2, crossover trial to evaluate the safety, efficacy, and patient quality of life of PureWick[™] System in comparison with Hollister® Female Urinary Pouch. Participants are randomized 1:1 to use PureWick[™] System in phase 1 and Hollister® Female External Pouch in phase 2, or to use Hollister® Female Urinary Pouch in phase 1 and PureWick[™] System in phase 2. Each phase lasts 4 weeks, with a 2-4 week washout period between phase 1 and phase 2. Capture rates and Draize Scale are assessed daily during both phases. Nocturia-Quality of life is assessed at baseline and every 14 days during phases 1 and 2. PROMIS Sleep disturbance is assessed at baseline and every 7 days during phases 1 and 2. User preference questionnaires are completed at the completion of each treatment phase with final user preference between the PureWick[™] System and Hollister® Female Urinary Pouch External Collection Device after completion of both treatments. The primary efficacy endpoint is the mean of daily capture rate. The primary safety endpoint is the mean of daily assessments of Draize Scale.

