5.2.3.3 Tolerability - Number of days of actual use

The calculation for the number of days of actual use will involve counting the non-missing records for each device, determined by the number of non-missing Day # entries. Subsequently, the number of days of actual use will be summarized using descriptive statistics by treatment. Paired differences between treatments will also be provided.

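### SAP 7.0 shows adverse events by device phase without time at risk, so the figures can understate events on the device stopped more often

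*SAP*

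**What the plan says.** SAP 7.0 groups adverse events (AEs) and serious adverse events by device phase: "the PureWick Phase includes all AEs/SAEs that occurred during the PureWick treatment phase". The same rule is given for the Hollister device. Events with onset in the washout are to "be included in the analysis for the device used in Phase 1 treatment if treatment was performed for phase 1". Where a woman was treated in only one phase, her events go to that phase. The section names no denominator, person-time or rate, and Protocol section 10 plans no AE rate either.

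On length, SAP 2.1 states: "Each phase lasts 4 weeks, with a 2-4 week washout period between phase 1 and phase 2". Several rules can shorten a phase. Under Protocol 7.2.7 a Draize score of 4 in any category must be recorded as an AE and "will require participants to discontinue from the treatment phase"; washout then starts at once. SAP 5.2.3.4 makes failure to complete a phase for discomfort or inconvenience an endpoint. Protocol 7.2.16 re-screens eligibility before Phase 2, and SAP 7.0 itself provides for women treated in one phase only.

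SAP 5.2.3.3 derives wear time for each device by counting non-missing day entries, after which "the number of days of actual use will be summarized using descriptive statistics by treatment". It appears there as a tolerability summary and is not linked to the AEs.

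**The concern.** The AE results of the two devices will be read side by side. If one device is stopped more often, it collects fewer nights of wear and fewer daily nurse visits at which an event can be found. At the same nightly risk it then shows fewer events, and a reader could take the shorter exposure for better safety. Stopping may itself reflect poor tolerance, so the distortion can favour the less tolerated device.

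A woman who never starts the second device removes all 28 nights from that device, whatever the reason. The shorter window then falls on the device not started.

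The plan says that the data should support reimbursement and inform a later randomized trial, so the AE table needs a denominator that can be interpreted.

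**Working it through.** **Inputs from the documents.** About 30 women (SAP 2.4), 28 nights per device and a washout of 14 to 28 days (SAP 2.1), 1:1 allocation to sequence (SAP 2.3). The documents give no AE rate and no stopping rate.

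**Assumptions.** All 30 women start both devices. A fraction f stops one device after k nights for a reason that is not an AE, and nobody stops the other. The nightly hazard h is constant and equal on both devices. Stops are spread evenly over the two phases.

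**Step 1, design check.** 28 + 14 + 28 = 70 days, or 10 weeks, which agrees with women being "followed for approximately 10 weeks through 2 treatment phases". With the longest washout, 28 + 28 + 28 = 84 days, or 12 weeks. The plan states no AE exposure figure to reproduce.

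**Step 2, on-device nights.** Full use is 30 × 28 = 840 nights. Take f = 20% and k = 7, a stop at the Day 8 visit: 24 × 28 + 6 × 7 = 714 nights. The ratio is 714/840 = 0.85, so 15% fewer events are expected at equal hazard. The nightly rate on the stopped device would have to be 840/714 = 1.18 times as high to give the same count.

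**Step 3, with washout counted as SAP 7.0 directs.** Fifteen women use each device in Phase 1. Off-device days are given the same hazard.

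| Washout | Added to each device | Stopped device | Other device | Ratio |
|---|---|---|---|---|
| 14 days | 15 × 14 = 210 | 714 + 210 = 924 | 840 + 210 = 1,050 | 0.88 |
| 28 days | 15 × 28 = 420 | 714 + 420 = 1,134 | 840 + 420 = 1,260 | 0.90 |

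The shortfall becomes 12% or 10%. For a single woman who stops after 7 nights, the window is 7 v 28 days in Phase 2. In Phase 1 it is 21 v 42 days (14-day washout) or 35 v 56 days (28-day washout).

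**Step 4, percentage of women with an event.** Assume that 20% of full-phase users have an AE, so h = −ln(0.80)/28 = 0.00797 per night. A woman with 7 nights has an event with probability 1 − 0.80^(7/28) = 5.4%. The stopped device shows 0.80 × 20% + 0.20 × 5.4% = 17.1%, against 20%. Expected counts are 714 × 0.00797 = 5.7 and 840 × 0.00797 = 6.7, a difference of about one event.

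**Step 5, stops that are themselves AEs.** Suppose instead that every AE ends the phase. The percentage stays at 20%, because each stopped woman already has her event. Only later events are lost: 30 × 0.20 = 6.0 events, against 6.7 with no stopping.

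**Step 6, range.** The on-device count ratio is 1 − f(1 − k/28). It runs from 0.95 (f = 10%, k = 14) to 0.625 (f = 50%, k = 7). At f = 30% and k = 7 the nights are 651 v 840 (ratio 0.775), and a true nightly rate ratio of 1.25 appears as 1.25 × 0.775 = 0.97, so the order reverses. At f = 0 the ratio is 1.

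**Step 7, after the fix.** With equal hazard, both devices in Step 4 show 0.80 events per 100 device-nights, whatever the stopping pattern.

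**The case against.** The strongest objection is that the table shells and the derived-data specification (SAP Appendices 1 and 2) are listed but not in the supplied text, and AE denominators could be set there. That stands: a reader might infer that the plan makes no allowance anywhere, but only the visible text of section 7.0 can be judged.

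Four other stronger readings are tempting and are not supported:

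- *That the primary safety result is biased.* That endpoint is the mean Draize score over assessed days (SAP 5.2.2.2), so fewer nights do not mechanically lower it. The point concerns AEs, which are not listed as an endpoint.
- *That every percentage is biased.* A Draize 4 stop is itself an AE, so it does not lower the share of women with an event (Step 5).
- *That observation ends when a device is stopped.* The sentence "At the time of discontinuing from the study, no further assessments will be performed" concerns leaving the study. A woman who stops the first device for a Draize 4 enters washout, and her washout events still count for that device.
- *That the AE table would show 15% fewer events.* That figure is for on-device nights alone and leaves out the washout rule. Washout is only a partial offset: it does nothing for a Phase 2 stop, it adds off-device days, and the schedule shows no skin assessment in that column.

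It is also fair that this is a descriptive pilot with no formal test, that Protocol 8.1 expects study withdrawal to be uncommon, and that days of use, phase non-completion and reasons for discontinuation are reported elsewhere. A careful reader could set exposure beside the AEs, but the plan does not do so for them.

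**Conclusion.** The point holds for AEs and serious AEs as section 7.0 is written. Event counts, and percentages where the stop is not itself an AE, can understate events on the device stopped more often.

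The size is conditional. With 20% stopping one device after 7 nights and none stopping the other, the shortfall is 15% of on-device nights, or 10 to 12% of days under the washout rule. In absolute terms, if 20% of full-phase users have an AE, that is about one event and fewer than one woman in 30. It grows with earlier or more frequent stopping and vanishes with none. All stopping and event rates here are assumptions, as are the constant hazard and the equal hazard off the device. This is a worthwhile and inexpensive reporting improvement; it does not undermine the primary analysis.

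**What to change.** In SAP 7.0, keep the number and percentage of women with an event, and add for each device:

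- the device-nights worn, taken from the days-of-use variable in SAP 5.2.3.3. Check it against nights actually worn, since it counts day entries and a phase has visits beyond its 28 nights;
- the AE rate per 100 device-nights for events with onset while on the device, with numerator and denominator from the same women and the same nights.

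Keep the present washout attribution in the main table. Also show washout-onset events on a separate line and leave them out of the per-night rate, so that no event is lost. If the table shells already carry exposure, a sentence in section 7.0 pointing to them may be enough.

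The cost is SAP wording, one extra column and line, and the check on nights worn. The rate assumes a roughly constant nightly hazard and is less familiar than a percentage, which is why both are shown.

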7.2.13 Days 23-28

1. Same procedures as days 2-7.

7.2.14 Day 29

- 1. Same procedures as days 2-7 with the exception of steps 6 and 7.
- 2. Participant to complete 4-week N-QOL assessment.
- 3. Participant to complete Day 29 PROMIS Sleep Disturbance assessment.
- 4. Participant to complete comfort and ease of use questionnaires.
- 5. If this day is the last day of phase 1 treatment for the participant, they will begin washout and prepare for phase 2 treatment.
- 6. If this day is the last day of phase 2 treatment for the participant, they will complete the study. Participant is to complete the End of Study Preference Survey.

7.2.15 Day 30

The participant will be asked to report any discomfort or voiding issues occurring within the first 24 hours after treatment phase completion or discharge from the study to the PI or sponsor. Skin assessments will also be conducted 24 hours after the participant completes the treatment phase and/or the study.

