2.3 Randomization and Blinding

Subjects will be randomized 1:1 to the two sequences of treatment (using PureWick[™] FECs in phase 1 and Hollister® Female External Pouch in phase 2, or the reversed order). This design allows the evaluation of elements such as the carryover effect, period effect, and sequence effect. To begin treatment phase in either the U.S. or France, using a prepared randomization schedule participants will be randomized 1:1 to use either PureWick[™] FEC in phase 1 and Hollister® FUP in phase 2, or vice versa. Block randomization will be carried out using a fixed block size of 2 and stratified by investigational site and geography.

This is an open-label study. Blinding is not applicable.

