2.4 Sample Size

Approximately 30 participants will be enrolled. The sample size is planned based on operational and practical considerations and is adequate for the purpose of this pilot study.

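### SAP 7.0 can count an adverse event under a device the woman had not yet worn, and it pools washout events with the Phase 1 device over an unequal window

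*SAP*

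**What the plan says.** SAP 7.0 (Safety Analysis) has three assignment rules.

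1. Events during a treatment phase count for the device of that phase: "the PureWick Phase includes all AEs/SAEs that occurred during the PureWick treatment phase", and likewise for Hollister.
2. Washout events will "be included in the analysis for the device used in Phase 1 treatment if treatment was performed for phase 1".
3. For a woman with an untreated phase: "If treatment was not performed in one of the phases, the AEs will be included in the other phase where treatment was performed".

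The timing comes from SAP 2.1: "Each phase lasts 4 weeks, with a 2-4 week washout period between phase 1 and phase 2". Protocol 7.2.15 (Day 30) asks participants to report discomfort or voiding problems "within the first 24 hours after treatment phase completion or discharge from the study", and adds: "Skin assessments will also be conducted 24 hours after the participant completes the treatment phase and/or the study". After Phase 1 that check falls inside the washout. After Phase 2 it is the last planned contact. SAP 7.0 does not say where an event with onset after Phase 2 is counted.

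**The concern.** Rule 3 works in both directions and has no onset condition. If Phase 2 was the untreated phase, later events move back to a device already worn. If Phase 1 was the untreated phase, events move forward to a device not yet worn, and an event that precedes first use cannot be an effect of that device.

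Rule 2 raises a separate matter. Whichever device comes first is charged with two to four device-free weeks, while the second is followed for about a day after its phase. Background events from those weeks appear in the device columns with nothing to mark them.

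The by-device AE table would be affected. Comparing the safety of the two devices is part of the primary objective (SAP 1.2), and the pilot is meant to support reimbursement and the planning of a later randomised trial (SAP 1.1).

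**Working it through.** The documents give no AE rate or exposure figure, so there is nothing to reproduce. The check has two parts.

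**A. Can an event be counted before exposure?**

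- Randomisation takes place at screening (Protocol 1.3). Treatment starts only if the Day 1 skin score is 0 (Protocol 7.2.6). A randomised woman can therefore miss Phase 1 treatment, and SAP 6.1 counts women randomised and not treated.
- AEs are collected before treatment, even for screen failures (Protocol 5.4).
- The proviso in rule 2 shows that the SAP foresees an untreated Phase 1. For such a woman rule 2 does not apply, so rule 3 sends her Phase 1 events, and probably her washout events, to the Phase 2 device.
- Size per woman, if she is observed over a nominal Phase 1 and washout: 28 + 14 = 42 to 28 + 28 = 56 pre-device days. Against 30 × 28 = 840 on-device days per device, that is 42/840 = 5.0% to 56/840 = 6.7%.

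**B. What does pooling the washout do?**

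Inputs: "Approximately 30 participants will be enrolled" (SAP 2.4), taken as 30; 28-day phases; washout of 14 to 28 days; one day after Phase 2. Assumptions: all phases completed and a constant background rate.

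| Quantity, sequences 15:15 | 14-day washout | 28-day washout |
|---|---|---|
| Days charged, Phase 1 device (28 + washout) | 42 | 56 |
| Days charged, Phase 2 device (28 + 1) | 29 | 29 |
| Total per device (15 × Phase 1 + 15 × Phase 2) | 1,065 | 1,275 |
| On-device days (30 × 28) | 840 | 840 |
| Device-free days | 225 (21%) | 435 (34%) |

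If the Phase 2 window is taken as 30 days and only the washout counts as device-free, the lower end is 14/(42 + 30) = 19%. The range is therefore about 19% to 34%. Both devices have the same total, so the between-device ratio of days is 1.00.

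*Dilution.* Suppose one device truly has twice the on-device event rate of the other, and washout events occur at the lower (background) rate. In units of background events, leaving out the single day after Phase 2:

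- 14-day washout: (840 × 2 + 15 × 14)/(840 + 15 × 14) = 1,890/1,050 = 1.80.
- 28-day washout: (840 × 2 + 15 × 28)/(840 + 15 × 28) = 2,100/1,260 = 1.67.

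The absolute difference is 840 in both cases, the same as on-device (1,680 − 840).

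*Imbalance.* SAP 2.3: "Block randomization will be carried out using a fixed block size of 2 and stratified by investigational site and geography". Each site can be out of balance by at most one woman. With about four sites (Protocol synopsis) the widest split of 30 is 17:13.

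- 14-day washout: (17 × 42 + 13 × 29)/(13 × 42 + 17 × 29) = 1,091/1,039 = 1.05.
- 28-day washout: (17 × 56 + 13 × 29)/(13 × 56 + 17 × 29) = 1,329/1,221 = 1.09.

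With two sites, as Protocol 4.1 has it, the widest split is 16:14, giving 1,078/1,052 = 1.02 to 1,302/1,248 = 1.04.

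*With an equal window* of 29 days in each phase, each device has 30 × 29 = 870 days whatever the split. A true ratio of 2 then shows as (1,680 + 30)/(840 + 30) = 1.97.

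**The case against.** The best defence is that the SAP states its rules in advance and that most of them are reasonable. Linking a washout event to the last device worn is a usual crossover convention. It catches delayed skin effects, and the Phase 1 Day 30 check itself lies in the washout. Each device comes first for about half the women, so the extra days nearly cancel between devices. The table is descriptive, in a pilot with no formal test, and every AE record carries a start date and a relationship to device (Protocol 9.4), so events can be re-sorted. The table shells and derived-data specification (SAP Appendices 1 and 2) are not in the public text and may already separate some of this.

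Most of that stands, and it rules out three stronger readings that a reader might infer.

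- *Device AE counts are wrong in general.* For a woman treated in Phase 1, none of the rules moves an event to a device not yet worn. The fault needs Phase 1 untreated and Phase 2 treated. Protocol 7.2.6 makes a woman ineligible for treatment if she does not reach a skin score of 0 within four weeks of the original baseline visit, so the pattern may be rare or absent.
- *Every event moved by rule 3 is misattributed.* When Phase 2 is the untreated phase, the event goes to a device she had already used, and a delayed effect is possible.
- *The washout rule favours one device.* At equal sequence sizes it does not. A split wider than 17:13 cannot come from randomisation with about four sites. It would need unequal dropout, for which the documents give no figure.

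The defence does not answer the missing onset condition, which balanced sequences cannot repair, or the loss of relative contrast, which remains at 15:15.

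**Conclusion.** The point holds in two parts. First, rule 3 as written gives a wrong assignment for any event that precedes first wear in a woman untreated in Phase 1 and treated in Phase 2. The number of such women is unknown; each could add pre-device time equal to 5.0% to 6.7% of the Phase 2 device's on-device days. Second, pooling washout events is a defensible link but an unhelpful presentation. It weakens a relative contrast rather than creating one, and adds at most a 5% to 9% difference in days charged from randomisation imbalance.

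These sizes assume 30 women, completed phases and a constant background rate. They are shares of days, not of events. The primary safety endpoint, the mean daily Draize score by phase, does not use these rules and is unaffected. The change is worth making because it is cheap and the by-device AE table will be read as a comparison of the devices.

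**What to change.** 1. Limit the untreated-phase rule to events with onset on or after first placement of the device under which they are counted. List earlier events as 'before device exposure'.
2. Show washout events in their own column or row, with the preceding device noted. Base the main by-device comparison on the same window in both phases, from first placement to the Day 30 check, and say how the window closes for a woman who stops early.
3. State where events with onset after Phase 2 are counted.

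The cost is SAP wording and one extra table column; AE start dates are already collected. The trade-off is that some delayed events move from the main device column to the washout column, where they stay visible. If the analysis has already been run under the present SAP, Protocol 10.0 allows the change to be described and justified in the clinical study report.
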